10.6.3 Transcranial Doppler (TCD) Sub-Study

Centres that have the appropriate equipment can also perform TCD recordings on patients recruited to CADISS in order to ascertain whether treatment with anticoagulation, or with antiplatelet therapy, is more effective at reducing asymptomatic embolisation. For patients recruited to CADISS who also consent to the TCD sub-study the following additional investigations will be performed.

Transcranial Doppler recordings for embolic signals will be performed from the ipsilateral middle cerebral artery (MCA; for carotid dissection) and from the ipsilateral posterior cerebral artery (PCA; for vertebral dissection) for a period of one hour immediately after randomisation but prior to commencement of study treatment. Recordings will be repeated on day 7 (at the same time of day as the initial recording +/- two hours). The MCA and PCA should be identified via the transtemporal window, and the transducer fixed in position using a headset.

All recordings will be made onto digital audio tape or other suitable digital media. Recordings will then be analysed at St George's for the presence of embolic signals by an experienced investigator. Standard criteria will be used to identify embolic signals⁽⁴⁾. Embolic signals ≥ 7 dB will be identified as these have been shown to associate with increased risk of recurrent stroke in previous studies.

Single channel transcranial Doppler recordings will be performed. Transcranial Doppler equipment can only be used if the output can be analysed by the central reading station at St George's. Suitable equipment includes the following:

1. Nicolet/EME Pioneer TCD systems with analogue signal being recorded onto digital audio tape.
2. DWL systems with analogue output being recorded onto digital audio tape.
3. Digital Nicolet/EME systems with digital output being recorded onto CD.

Digital systems other than the EME system cannot be used as the data cannot be read centrally. Analogue systems other than DWL and TCD should not be used until similarity of the Doppler to the systems being used in the study have been determined.

Patients will be treated as their own control and the primary endpoint will be the reduction in embolic signals. Secondary endpoint will be the abolition of embolic signals (i.e. a negative recording).

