4.2 Investigational Medicinal Product (IMP)

(a) Antiplatelet therapy: Aspirin, dipyridamole or clopidogrel alone or in dual combination.

(b) Anticoagulation with heparin (either unfractionated heparin or a therapeutic dose of low molecular weight heparin) followed by warfarin aiming for an INR in the range 2-3. Local protocols for heparin therapy can be used.

Treatment will be open-label.

Low dose heparin prophylaxis for prevention of DVT is not a contra-indication, but its use should be recorded. Such prophylaxis may be continued after randomisation in the antiplatelet arm at the discretion of the local clinician.

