9.2 Randomisation procedure

Randomisation will be via an automated 24 hour randomisation service provided by the University of Aberdeen Health Services Research Unit. The local investigator or delegated person will personally contact this service on [name] along with the trial ID code specific for each centre, known only to the randomisation centre and local investigator. During the call you will also be required to enter the patient's initials. Once this information has been submitted you will receive a randomisation code and a treatment allocation stating either "anticoagulants" or "antiplatelets." Once randomised into the study, all patients will be included in an "intention to treat" analysis.

In the unlikely event of a system failure where you are unable to contact the automated randomisation service you should call the back-up number [name] or perform a manual randomisation by flipping a coin. Please assign a treatment arm to each side of the coin and ask an independent person to flip the coin. Please retain accurate records regarding the event. If you perform a manual randomisation please contact the trial coordinator as soon as possible so that the randomisation details can be passed on to the University of Aberdeen who will update the system retrospectively.

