10.5 Summary flow chart of study assessments

Study Procedures	Screening	Following Randomisation: Treatment Initiation	Follow up (3 mnths)	Follow up (6 mnths)	Follow up (12 mnths)
Informed consent	X				
Inclusion/exclusion criteria	X				
Medical history	X				
Demographics	X				
Baseline	X				
Screening	X				
Biochemistry	X Cholesterol Only				
Imaging: MRI dissection views, MRA, CTA, or intra-arterial angiography	X		X		
Telephone call				X	X
Dispensing/Administration of IMP		X			
Concomitant Medication	X		X	X	X

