11.4 Route of administration, dosage, dosage regimen, and treatment period(s) of the IMPs

The dose and frequency of IMP should reflect local policy and NICE guidelines.

CADISS patients should be given IMP from the time of randomisation until their three month follow-up appointment. After this time, the treatment choice is at the discretion of the prescribing physician and the patient should begin taking non-IMP.

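### The TCD sub-study makes its baseline recording after the open-label allocation is known and does not require consent before it, so who contributes data can depend on the arm

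*Protocol*

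**What the plan says.** Section 10.6.3 offers an optional Doppler sub-study in centres with suitable equipment. Its aim is comparative: which of the two treatments does more to reduce silent embolisation. Entry is by additional consent: "For patients recruited to CADISS who also consent to the TCD sub-study the following additional investigations will be performed". The one-hour baseline recording is made "immediately after randomisation but prior to commencement of study treatment", with a repeat on day 7. On the endpoint the section says: "Patients will be treated as their own control and the primary endpoint will be the reduction in embolic signals".

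Three other places bear on the timing:

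- Section 4.2: "Treatment will be open-label".
- Section 9.2 tells the person making the randomisation call that "you will receive a randomisation code and a treatment allocation stating either" one treatment or the other.
- Section 11.4: "CADISS patients should be given IMP from the time of randomisation until their three month follow-up appointment".

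The flow chart in section 10.5 has a column headed "Following Randomisation: Treatment Initiation". It gives no interval between the two steps and has no row for the Doppler recordings.

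**The concern.** A change-from-baseline endpoint in a randomised comparison is best protected when both the decision to take part and the baseline itself are settled before anyone knows the arm. Here the baseline comes after disclosure, and participation may do so too. A clinician who knows the arm may be more or less inclined to offer the sub-study, or to hold back treatment for an hour while the recording is made. A patient who knows the arm may respond differently to the request.

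If such decisions differ between arms, the patients with a usable baseline are no longer two random samples of the same population. At stake is the between-treatment comparison that the sub-study exists to make.

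**Working it through.** The protocol states no sample size, signal rate, uptake or missing-data rate for the sub-study. There is therefore no figure to reproduce, and the check is a comparison of sections.

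**1. Order of events.** Section 6.4 runs from eligibility, information and trial consent to the randomisation call, and then to the entry form and the prescription. It contains no Doppler step. By section 9.2 the call itself discloses the arm, and by section 4.2 nothing conceals it afterwards. Section 10.6.3 then places the recording. For a sub-study patient the sequence is: trial consent, call and disclosure of the arm, baseline hour, study treatment, day-7 recording. Sub-study consent has no fixed place in it.

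**2. What can depend on the arm.**
- *Entry.* Section 10.6.3 speaks of patients recruited to the trial who also consent, and does not tie that consent to a time before the call. Asking after the call would breach nothing.
- *Completion.* Even where consent came earlier, the recording starts when the arm is known. Leaving it out would depart from 10.6.3, but the decision would be made with knowledge of the arm.

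**3. Whether this reaches the endpoint.** A patient with no baseline has no reduction to measure and drops out of the primary endpoint. Using patients as their own controls removes stable differences between patients from each measured change. It does not restore comparability between arms if different kinds of patient are measured in each.

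**4. Form of the bias.** Take as the target the patients who would have entered had entry been settled before allocation. In arm *a*, let p_a be the proportion of them with a baseline. Let m_a be the mean reduction among those with a baseline, and n_a the mean that those without one would have shown.

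- Mean for the whole arm: p_a × m_a + (1 − p_a) × n_a
- Observed mean: m_a
- Error in arm *a*: m_a − [p_a × m_a + (1 − p_a) × n_a] = (1 − p_a)(m_a − n_a)
- Error in the comparison of arms A and B: (1 − p_A)(m_A − n_A) − (1 − p_B)(m_B − n_B)

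The error is zero if every such patient has a baseline, or if those with and without one would respond alike. It also cancels if the two arms lose the same proportion with the same difference in response. The protocol supplies none of p, m or n for either arm, so neither size nor direction can be stated.

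**5. Sections 10.6.3 and 11.4.** Section 11.4 counts treatment from randomisation and makes no exception for sub-study patients. Read to the minute, that leaves no untreated hour. Read as the overall treatment period, which is part of what its heading announces, it is compatible with 10.6.3. Sections 6.4 and 10.5 support the second reading, since they show prescribing and treatment initiation as steps after the call.

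**The case against.** The strongest reply is that the plan is reasonable as it stands. Section 10.6.3 requires the hour for every consenting patient, so a missing recording is a failure of conduct. Sub-study consent may in practice be taken together with trial consent, before the call. Recordings are analysed centrally to standard criteria, so the operator who knows the arm does not count the signals. The sub-study is optional and feeds none of the endpoints in section 15.2.

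Much of this stands and limits the point. The protocol does not show that selection will occur, and the scope is small. Central analysis, however, governs how signals are counted and not whether a recording exists. Joint consent would close the entry route but leave the recording after disclosure. Nor can an analysis plan recover a baseline that was never made.

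Two stronger readings are tempting and are not supported:

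- *That 10.6.3 and 11.4 cannot both be followed.* A site can follow both if 11.4 gives the overall treatment period. The wording conflicts only when 11.4 is taken literally.
- *That the baseline is contaminated by study treatment.* Section 10.6.3 itself requires the recording before treatment starts, so contamination would need a deviation or a literal use of 11.4. Nothing in the protocol says that one arm would start treatment sooner. Antithrombotics already in use at entry, which section 6.1 allows, precede allocation and are balanced between arms in expectation.

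**Conclusion.** The point holds in a limited form. Because the arm is disclosed before the baseline hour, and sub-study consent is not required before disclosure, entry and completion can depend on the arm. That leaves the between-arm comparison of the reduction in embolic signals open to post-randomisation selection.

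The conclusion rests on three things the protocol states (open-label treatment, disclosure in the call, recording after randomisation) and on its silence about when sub-study consent is taken. For actual bias one must further assume that staff or patients act on the arm, and that those lost would have responded differently from those kept. Neither is established, and no size can be given. A reader might want to attach a percentage, but it would rest wholly on assumed signal counts and omission rates.

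Severity is minor. The baseline is placed where it is less protected than it could be, which is not an error, and only the sub-study is concerned. The trial's feasibility objectives (section 5.1) and clinical endpoints (section 15.2) are unaffected.

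**What to change.** Amend section 10.6.3 so that sub-study consent is obtained and the one-hour baseline recording is completed before the randomisation service is called. Add the Doppler recordings to the schematic in 6.4 and the flow chart in 10.5 so that the order is visible to sites. Entry and baseline are then settled without knowledge of the arm. Loss of the day-7 recording can still depend on the arm, so it should be reported by arm.

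The cost is sub-study wording, a randomisation call that moves by about an hour in participating centres, and a few recordings in patients who are then not randomised. Section 10.6.3 already places the hour before study treatment, so the change alters the order of steps and adds no further recording.

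Separately, align 10.6.3 with 11.4 so that the two describe the start of treatment relative to randomisation in the same way. Which timing applies is for the clinical team to settle.

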4.1 Background

Dissection of the carotid and vertebral arteries is a major cause of stroke in persons <50 years of age, mainly due to embolism from clot sealing the tear. At present physicians treat these patients with anticoagulants or antiplatelet drugs to prevent further stroke, but neither therapy is evidence-based. Anticoagulants may be powerful anti-embolic agents but are also more hazardous than aspirin, and potentially could encourage further dissection. Most published studies are flawed by retrospective data, with no reference to the number of patients in the original study cohort and do not include the critical principles of randomisation and 'blinding' of outcomes.

The only prospective data available⁽¹⁾ suggests that anticoagulants are more effective than antiplatelet agents in reducing further TIA and stroke after dissection, but the numbers were small and lack reliable statistical confirmation. This study was not a randomised controlled trial and therefore may be open to bias in selection of treatment. In addition, it found that most recurrent events occur within the first month and thereafter the number tails off. A total of about 1800 patients would be required for a two armed trial comparing antiplatelet agents with anticoagulants calculated on these data.

Authors of a previous Cochrane review⁽²⁾ reviewing available published literature calculated that a total of about 2800 patients (1400 in each treatment arm) are needed for a blinded randomised trial of anticoagulants vs antiplatelet agents. This would need a major, probably international, study involving over 100 centres, and would be an expensive undertaking. Prior to starting such a study it is important to determine whether this would be feasible. This is particularly important for carotid and vertebral dissection which is a diagnosis frequently missed, at least during the acute phase. Limited natural history outcome data suggests the risk of recurrent stroke and TIA following carotid and vertebral dissection is only markedly raised during the first week to month^(1, 3) and therefore early identification and recruitment of patients is essential if any treatment effect is to be demonstrated.

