6.1 Overall design

This will be a randomised prospective multicentre study comparing antiplatelet therapy with anticoagulation for patients with carotid and vertebral dissection. Recruitment must be within seven days of onset of symptoms. Patients should not be precluded from randomisation if they are currently treated with antiplatelet or anticoagulant drugs.

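### The TCD sub-study asks which randomised treatment works better, but names the patient as the control and states no between-arm contrast

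*Protocol*

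**What the plan says.** Protocol section 10.6.3 gives the purpose of the sub-study as comparative: recordings are made "in order to ascertain whether treatment with anticoagulation, or with antiplatelet therapy, is more effective at reducing asymptomatic embolisation".

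The design and endpoints are then fixed as follows.

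- First recording: "for a period of one hour immediately after randomisation but prior to commencement of study treatment".
- Second recording: "Recordings will be repeated on day 7".
- Control and primary endpoint: "Patients will be treated as their own control and the primary endpoint will be the reduction in embolic signals".
- Secondary endpoint: "Secondary endpoint will be the abolition of embolic signals (i.e. a negative recording").

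Neither endpoint is tied to a comparison of the two arms. The between-group analysis in section 15.1 concerns time to an outcome event and does not mention the TCD recordings.

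Two other places bear on the point. On natural history, section 4.1 says that "the risk of recurrent stroke and TIA following carotid and vertebral dissection is only markedly raised during the first week to month" and that "most recurrent events occur within the first month and thereafter the number tails off". On earlier treatment, section 6.1 says: "Patients should not be precluded from randomisation if they are currently treated with antiplatelet or anticoagulant drugs".

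**The concern.** The question is about two treatments, and the patients are already randomised between them. The natural control for each arm is therefore the other arm. The protocol names the patient instead.

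An analyst who follows that sentence literally would test day 7 against baseline within each arm. Such a test answers whether signals changed, not which treatment changed them more. It also credits treatment with any change that would have happened anyway between the two recordings. Both arms could look effective, or one could reach significance and the other not, with no difference between the treatments.

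Two further features weaken the patient as a control. Because earlier antithrombotic treatment is allowed, the first recording need not be free of treatment. And a patient with no signals at baseline cannot show a reduction, yet may give a negative recording at day 7 without any treatment effect.

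**Working it through.** The protocol states no signal rate, sub-study size, alpha or power for this comparison, so there is no figure of its own to reproduce. The two possible readings are checked in turn. All numerical inputs below are assumptions unless a section is named.

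**Reading 1: before/after within each arm**

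Suppose both arms have the same true decline and each within-arm test has power p. The chance that exactly one arm is significant is 2p(1 − p):

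- p = 0.3: 2 × 0.3 × 0.7 = 0.42
- p = 0.5: 2 × 0.5 × 0.5 = 0.50 (the maximum)
- p = 0.8: 2 × 0.8 × 0.2 = 0.32

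Over p = 0.3 to 0.8 the range is therefore 32% to 50%.

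A simulation checks this with counts (4,000 runs per setting). Assumptions: gamma-Poisson counts with mean 4 per hour and gamma shape 0.5, the same proportional spontaneous decline in both arms, no treatment difference, two-sided 0.05, square-root counts. The within-arm test is the Wilcoxon signed-rank test. The between-arm test is the Mann-Whitney test on each patient's change.

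| Patients per arm | Spontaneous decline | Within-arm test significant | Exactly one arm significant | Between-arm test on change significant |
|---|---|---|---|---|
| 20 | 25% | 24% | 37% | 5.2% |
| 30 | 25% | 35% | 46% | 4.5% |
| 60 | 25% | 65% | 47% | 5.1% |
| 20 | 50% | 74% | 40% | 4.7% |
| 30 | 50% | 90% | 18% | 4.5% |
| 60 | 50% | 99.8% | 0.4% | 5.0% |

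Over all settings, including declines of 0% and 75%, the between-arm test rejected in 4.4% to 5.8% of runs. A decline shared by the arms cancels in that comparison.

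**Reading 2: change from baseline, compared between arms**

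This is valid, as the last column shows. The question is then precision. Let the baseline and day-7 values have equal variance σ² and correlation r.

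- Variance of the change score: 2σ²(1 − r)
- Variance after linear adjustment for baseline: σ²(1 − r²)
- Ratio: (1 − r²) / [2(1 − r)] = (1 + r)/2

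For r = 0.3, 0.5 and 0.7 the ratio is 0.65, 0.75 and 0.85, which is a reduction of 35%, 25% and 15%.

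Equal variances are doubtful for declining counts. With standard deviations σ0 and σ1, the two variances differ by (σ0² + σ1² − 2rσ0σ1) − σ1²(1 − r²) = (σ0 − rσ1)², which is never negative. The sizes depend on equal variances. The direction does not, apart from the small cost of estimating the slope.

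**Patients with no baseline signals**

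Under the simulation's count assumption, the share with a zero baseline is [0.5/(0.5 + 4)]^0.5 = (1/9)^0.5 = 1/3. This describes the assumption, not the trial, but it shows that the group need not be small. None of these patients can show a reduction.

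**Is early decline likely?**

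Section 6.1 requires recruitment within 7 days of symptom onset. If day 7 is counted from randomisation, the second recording falls about 7 to 14 days after onset. Section 4.1 places the raised risk in the first week to month, so some decline by then is plausible. That section speaks of stroke and TIA, however, not of embolic signals. Its remark that events tail off refers to the time after the first month, which is later than day 7.

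**The case against.** The strongest reply is that section 10.6.3 defines endpoints and names no test. Its opening sentence sets a comparison of the treatments as the purpose. On a natural combined reading, each patient's day-7 recording is set against that patient's own baseline, and the resulting reductions are compared between the randomised arms. Spontaneous decline and regression to the mean then act on both arms alike and cancel. The model, the baseline adjustment and the handling of zero baselines can be left to the SAP, which is not at hand. The sub-study is also optional and lies outside the trial endpoints in section 15.2 and the feasibility objective in section 5.1.

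Much of this stands. A reader might infer that the protocol discards the randomised comparison, or that it prescribes a before/after test. The text supports neither: it never excludes a between-arm comparison, and its aim implies one. A reader might also infer from section 4.1 that signals are bound to fall by day 7. That section makes a fall plausible and no more. The 32% to 50% figure presupposes two separate within-arm tests that the protocol does not describe.

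What does not fall away is the wording itself. The protocol is not silent on the control. It names one that does not match its question, and leaves the matching contrast unstated. An SAP could follow that sentence faithfully and still not answer the question.

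**Conclusion.** The point holds as a mismatch between question and stated control. Read literally, the sentence gives a before/after analysis that cannot attribute change over the week to treatment or say which treatment is better. Read as change from baseline compared between arms, it is valid but less precise than a baseline-adjusted comparison.

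The discordance and simulation rates illustrate the literal reading only and rest on assumed power, counts and arm sizes. The variance reductions belong to the second reading and rest on equal variances and assumed correlations. The conclusion that the wording should change depends on none of these figures.

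The consequence is confined to the sub-study.

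**What to change.** In section 10.6.3, replace the sentence that makes patients their own control, and the secondary-endpoint sentence after it, with:

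> Day-7 embolic-signal counts (primary) and presence of any embolic signal at day 7 (secondary) will be compared between the randomised arms as allocated, adjusted for the baseline recording; within-patient change is descriptive.

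This settles both readings. It also gives patients with no baseline signals a defined place in the analysis, since their day-7 result counts and their baseline is adjusted for. The choice of model, for example negative binomial or a rank-based ANCOVA if counts are sparse, can stay with the SAP.

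The cost is a short text change. The recordings and patients stay the same.
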